**NCT Number: under process**

**Date: 22 Aug 2020 to 21 Feb 2021**

**Study Protocol:**

**Objective:** Comparison of tazarotene gel 0.1% versus microneedling in atrophic post-acne scars.

**Design:** Randomized Control Trial.

**Duration:** Dermatology department, Jinnah Postgraduate Medical Centre (JPMC) Karachi, from August 22, 2020 to February 21, 2021.

**Methodology:** Patients aged 18-40 years were randomly divided into two groups having 101 patients in each group. Dermoscopic examination for scar type (such as icepick, rolling or boxcar) and scar severity assessed with Goodman and Baron acne scarring scale for every patient. In group A (tazarotene gel), patients were guided to put tazarotene gel 0.1% on scars everyday having pea-sized gel quantity with the help of finger tip on face. In group B, use a dermaroller (192 needles of length 1.5 mm), monthly for a period of 6 months. Saline pads were used post session. We recorded alteration from baseline in scar severity grade at follow up of 3 then 6 month. All collected data was entered into the proforma.

**Results:** Out of 202 patients, the mean age was  $26.3 \pm 5.8$  v.s  $25.2 \pm 5.5$  years, while 36 (35.6%) males and 65 (64.4%) females v.s 33 (32.7%) males and 68 (67.3%) females. Potency of gel 0.1% in 37 (36.6%) v.s microneedling in 31 (30.7%) patients ( $p=0.372$ ).

**Conclusion:** Tazarotene gel 0.1% efficacy was comparable to microneedling in treating atrophic post-acne scars.

**Key Words:** Efficacy, Topical Tazarotene Gel, Microneedling, Acne Scars, Treatment.

**INTRODUCTION**

Acne vulgaris is a long term inflammatory disease of the pilosebaceous. It has high grade existence and is known to negatively influence quality of life [1]. It begins in adolescence with 30% to 100% popularity. Acne scarring is popular and well-recognized outcome of acne [2-3]. It may be either atrophic or hypertrophic, further categorized morphologically into boxcar, icepick or rolling with the option of treatment modalities often based on scar types [4]. Prior recognition and control of acne is necessary in averting scarring and resultant unfavorable social effects developed due to irritation and feeling of being ashamed [5]. Acne scars developed due to inadequate treatment or delayed healing of inflammatory acne lesions [6]. Gels of retinoids, like adapalene, raises collagen by stimulating fibroblast cells [7]. A home-based topical treatment is more accepted and would be suitable in treating scars [8].

Another research has shown the better results of tazarotene gel 0.1% with contrast to adapalene 0.1%, in controlling acne [9]. The aim of our study is comparison of daily use of tazarotene gel 0.1% in contrast to performing derma roller monthly sessions for controlling acne scars. Many previous studies reported, but there was lack of local researches in head to head

comparison between these two therapies, to improve outcome by adopting superior approach as first choice of treatment in future.

### **METHODOLOGY**

This was a randomized Control Trial, done in Department of Dermatology, Jinnah Postgraduate Medical Centre (JPMC), Karachi from August 22, 2020 to February 21, 2021.

A total of 202 patients with 101 in each group. We estimated sample size using WHO calculator using statistics for efficacy in topical Tazarotene gel (group A) as 30.5% and micro-needling (group B) as 47.2%, 80% power of test and 95% confidence level. Both genders, 18 to 40 years with atrophic post-acne scar patients of duration 4 to 8 years were included. Informed consent was obtained. Patients of grade 4 to 2 were estimated by Goodman and Baron scarring scale. While excluded pregnant/lactating woman, any prior allergy to given drug, known case of having likelihood of past keloid, active acne or post macules of variable colors, previous dermabrasion, laser resurfacing on face, other causes of scarring, collagen disorders, coagulation disorders, past retinoid exposure below 4 weeks, hydroxy acids, microdermabrasion session below 3 weeks and retinoids taken orally in past 6 months.

This study was conducted after approval from ethical review committee and CPSP. During the patient first visit, baseline photographs were captured with informed consent. Dermoscopic examinations of predominant scar type (such as icepick, rolling or boxcar) and the scar intensity estimated by using Goodman and Baron scarring scale for every patient. Before the start of the work, a digital number was allotted from computer randomly to divide them into two groups. In group A, patients were guided to use a gel on scars everyday by putting a pea-sized quantity on index finger to conceal. Patients who complained dryness were instructed to use a moisturizer in morning but avoid any other medication on face. In group B, microneedling was carried out with dermaroller (192 needles and length 1.5 mm) by the similar doctor, one time in a month in total 6 monthly sessions. Before conducting dermaroller session, local anesthesia was put on scars containing lignocaine and prilocaine.

Microneedling was conducted by dermaroller in constant rolling motion with slight pressure in variable paths (i.e, diagonal and right angled direction) with upward motion till pinpoint bleeding was seen. After session, the saline soaked gauze were put on that area. The patients were also directed for precise use of sunblock having sun protective factor 30 on full area of face. All patients were followed up at 3 month and then at 6 month from the initial visit. Data stored in the form of pictures. Excellent score was labelled to those patients who uplift by 2 grades, while good for 1 and poor for 0 grade. The results were noted from alterations of initial scar grade first at 3 then at 6 month appointment. All data was entered in a predesigned proforma.

Biasness and confounder were controlled by strictly following the inclusion criteria.

SPSS 21 analysed the data. Frequencies and percentages were enumerated for qualitative data like gender, scar type, treatment, scar severity grade at baseline, after 3 and 6 months and efficacy. Quantitative variables were presented as mean  $\pm$  SD like age and duration of acne. Comparison between both groups for efficacy was done by using Chi square test. Modifier like age, gender and time span of disease were organised through stratification. Post stratification, Chi square test was used for categorical variables. Consider  $P \leq 0.05$  as significant.

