### **STATISTICAL ANALYSIS**

In this randomized control trial, the total of 202 patients 101 in each group were included to compare the efficacy between topical tazarotene gel 0.1% versus Microneedling in treatment of atrophic post-acne scars and results were analyzed as:

Mean $\pm$ SD of age in group A (topical tazarotene gel 0.1%) was 26.3 $\pm$ 5.8 with C.I (25.15----27.44) and group B (Microneedling) was

25.2 $\pm$ 5.5 with C.I (24.11----26.28) years, as shown in **TABLE 1**.

Mean $\pm$ SD for duration of acne in group A (Topical tazarotene gel

0.1%) and group B (Microneedling) was 6.5 $\pm$ 3.1 and 6.1 $\pm$ 2.6 with C.I

(5.88----7.11) and (5.88----7.11) years, respectively as shown in **TABLE 2**.

In group wise distribution of gender, 36 (35.6%) male and 65 (64.4%) females were enrolled in group A (Topical tazarotene gel 0.1%) while 33 (32.7%) male and 68 (67.3%) females were included in group B (Microneedling) as shown in **TABLE 3**.

In distribution for type of scar icepick was noted in 36 (35.6%) patients, rolling 14 (13.8%), boxcar 12 (11.9%) and mixed 39 (38.7%) patients in group A (Topical tazarotene gel 0.1%) while in in group B (Microneedling) icepick was noted in 40 (39.7%), rolling 15 (14.6%), boxcar 20 (19.9%) and mixed 26 (25.8%) patients as shown in **TABLE 4**.

Baseline scar severity grades 1,2,3,4 was noted in 0 (0%), 0 (0%), 20 (19.8%), 81 (80.2%) and 0 (0%),0 (0%), 20 (19.8%), 81 (80.2%) in group A and group B respectively. While at 3 and 6 months it was noted as 03 (3%), 12 (11.9%), 26 (25.7%), 60 (59.4%), 22 (21.8%),

67 (66.3%) and 03 (3%), 23 (22.8%), 26 (25.7%), 49 (48.5%), 03 (3%), 14 (13.9%), 24 (23.8%), 50 (59.4%) in group A and group B respectively as shown in **TABLE 5**.

Excellent grade was noted in 12 (11.9%) and 10 (9.9%) patients in group A and group B, respectively. Good grade was noted in 25 (24.8%) and 21 (20.8%) in group A and group B while poor grades was documented in 64 (63.4%) and 70 (69.3%) patients in group A and group B, respectively as shown in **TABLE 6**.

Topical tazarotene gel 0.1% was found to be effective in 37 (36.6%) patients while microneedling, was found to be effective in 31 (30.7%) patients with non-significant P value i.e. (P=0.372) as shown in **TABLE 7**.

Stratification of age group (18---25) and >25 years, gender (male & female) and duration of acne (4----6) > 6years were done to assess the significant difference between both groups from (**TABLE 8-10**).

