**COMPARISON OF EFFICACY BETWEEN BOTH GROUPS n=202**

GROUP	EFFICACY		P-VALUE
	Yes	No	
GROUP A	37 (36.6%)	64 (63.4%)	0.372
GROUP B	31 (30.7%)	70 (69.3%)	

Applied Chi-Square test

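### The stated 80% power does not apply to the two-sided chi-square test that was used; 101 per group gives that test about 69%.

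*Combined protocol and SAP*

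**What the plan says.** The METHODOLOGY section gives the enrolment as "A total of 202 patients with 101 in each group". It attributes this number to a WHO calculator, with efficacy in "topical Tazarotene gel (group A) as 30.5% and micro-needling (group B) as 47.2%, 80% power of test and 95% confidence level". It does not give the formula, the sidedness or an allowance for dropout.

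The same section sets the analysis: "Comparison between both groups for efficacy was done by using Chi square test", with P at or below 0.05 taken as significant. STATISTICAL ANALYSIS reports the result as "non-significant P value i.e. (P=0.372", and the footnote to Table 7 reads "Applied Chi-Square test".

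No direction is stated anywhere. The objective is a comparison of the two treatments, and the INTRODUCTION describes a head-to-head "comparison between these two therapies, to improve outcome by adopting superior approach as first choice of treatment in future", without saying which treatment is expected to win.

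**The concern.** A chi-square test on a 2x2 table counts a difference in either direction. Read beside such a test at 5%, a claim of 80% power with 95% confidence will be taken as two-sided 5%. On that reading, 101 per group looks too few for rates of 30.5% and 47.2%.

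The power statement is the only sample-size justification in the document. It also affects how the non-significant result is read, because the abstract and the CONCLUSION both describe the two treatments as similar in efficacy. A reader judging how much a null result means will look at the stated power. If that figure is too high, the trial appears better able to find a difference than it was.

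**Working it through.** **Inputs**

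- From METHODOLOGY: p1 = 0.305 (tazarotene), p2 = 0.472 (microneedling), n = 101 per group, power 80%, 95% confidence level.
- From STATISTICAL ANALYSIS and Table 7: 37/101 and 31/101 effective, P=0.372.
- No dropout allowance is stated, so 101 is taken as the analysed number per group.

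**Derived quantities**

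- Difference d = 0.472 − 0.305 = 0.167
- Mean rate = (0.305 + 0.472)/2 = 0.3885
- Pooled: s0 = √(2 × 0.3885 × 0.6115) = 0.6893
- Unpooled: s1 = √(0.305 × 0.695 + 0.472 × 0.528) = √0.4612 = 0.6791
- d√n = 0.167 × √101 = 1.6783

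**Formulas** (c is the critical value; 0.8416 corresponds to 80% power)

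- Pooled n = (c·s0 + 0.8416·s1)² / d²; power = Φ[(d√n − c·s0)/s1]
- Unpooled n = (c + 0.8416)²·s1² / d²; power = Φ[d√n/s1 − c]

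**Step 1: reproduce the plan's figure**

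With a one-sided 5% test, c = 1.645:

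- Pooled: n = 104.3; power at 101 = Φ(0.802) = 78.9%
- Unpooled: n = 102.2; power at 101 = Φ(0.827) = 79.6%

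This is close to the stated 80%, although neither formula returns exactly 101.

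**Step 2: the test that was used**

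With a two-sided 5% test, c = 1.960:

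- Pooled: n = 132.5, so 133; power at 101 = Φ(0.482) = 68.5%
- Unpooled: n = 129.8, so 130; power at 101 = Φ(0.511) = 69.5%
- Exact enumeration of the uncorrected chi-square test at 101 per group: 69.1%
- Arcsine formula: n = 132.2, so 133; power 68.8%

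A continuity correction widens the gap: 145 per group by formula, and an exact power of about 64% at 101.

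**Step 3: was the analysis two-sided?**

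For 37/101 against 31/101 the uncorrected chi-square is 0.798 on 1 degree of freedom, P = 0.3717. This matches the reported 0.372. With a continuity correction it would be 0.457. A one-sided P would be 0.814 in the planned direction (microneedling better) or 0.186 in the other. The reported test was therefore two-sided and uncorrected.

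**Step 4: size of the gap**

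- Shortfall for 80% power: 130 − 101 = 29 to 133 − 101 = 32 per group.
- Planned risk of missing the difference: 100% − 69% = 31%, against the stated 20%.
- Rates that 101 per group detects with 80% power, two-sided: 30.5% against 49.7% (pooled) or 49.4% (unpooled), a difference of about 19 points.
- Two-sided alpha at which 101 per group gives 80%: 0.108 (pooled) or 0.103 (unpooled).

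**The case against.** The strongest reply is that the calculation was probably one-sided. In that case the arithmetic is sound and the defect is an unstated setting. This is plausible: the one-sided formulas give 78.9% to 79.6%. If the rates are rounded to 30% and 47%, the pooled one-sided formula gives 100.3, hence 101. But the settings are not in the document, so it remains an inference. It also does not rescue the statement, because a one-sided sample size beside a two-sided test still claims power that the test does not have. Reading the figure as two-sided 10% would contradict the stated 95% confidence level and the P threshold.

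A second reply is that the trial is complete, so planning power matters little. Precision is now judged from the confidence interval. The observed difference (tazarotene minus microneedling) is 36.6% − 30.7% = 5.9 points. Its standard error is √(0.366 × 0.634/101 + 0.307 × 0.693/101) = 6.64 points, giving a 95% interval of about −7.1 to +18.9. That excludes the planned 16.7-point advantage for microneedling, but not an advantage of that size for tazarotene. This limits the consequence and stands as a limit. It does not make the stated power correct.

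A third reply is that a 19-point detectable difference was never a planning target. That is fair: if quoted, it should be labelled as a description of what 101 per group can detect.

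**Conclusion.** The concern holds. At the planned rates, with 101 per group and the two-sided uncorrected chi-square test at 5%, power is 68.5% to 69.5% (exact 69.1%), about 11 points below the stated 80%. Reaching 80% would have taken 130 to 133 per group, which is 260 to 266 in total instead of 202. None of the two-sided 5% methods tried brings the requirement near 101.

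This rests on the stated rates, the group size, the 5% threshold and the reported P-value, with no loss of patients; any loss would lower the power further. The mismatch follows from those figures. Only its cause, a one-sided setting, is inferred. No estimate, P-value or table is affected. The point should be fixed because the document claims power that the design did not have for its own test.

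**What to change.** Restate the sample-size paragraph along these lines: with 101 patients per group, a two-sided chi-square test at alpha 0.05 has about 69% power for 30.5% against 47.2%; 80% power is reached at about 30.5% against 49.7%, a difference of about 19 points. Label the second figure as a description of the achieved size, not as a planning target.

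Give the formula and the sidedness from the calculator record. If a one-sided 5% setting was used, keep that as the account of what was planned and say that it does not match the two-sided test in the analysis. Remove the 80% claim in its unqualified form.

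The cost is wording only: no new data and no re-analysis. The one downside is a less favourable stated power.

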**TABLE # 6**  
**DISTRIBUTION OF OUTCOME LEVEL n=202**

GROUP	OUTCOME LEVEL		
	Excellent	Good	Poor
Group A	12	25	64
	11.9%	24.8%	63.4%
Group B	10	21	70
	9.9%	20.8%	69.3%

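### Scar-grade change is recorded at months 3 and 6, but the single responder result names no visit; the 3-month responder outcome is unreported, and Table 5 only bounds it

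*Combined protocol and SAP*

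**What the plan says.** The Methodology paragraph of the Study Protocol summary states: "We recorded alteration from baseline in scar severity grade at follow up of 3 then 6 month". The METHODOLOGY section defines the outcome scale: "Excellent score was labelled to those patients who uplift by 2 grades, while good for 1 and poor for 0 grade". Its next sentence applies the scale at both visits: "The results were noted from alterations of initial scar grade first at 3 then at 6 month appointment". Neither visit is called primary.

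The analysis text in the same section promises two things that matter here. One is descriptive, frequencies and percentages for "scar severity grade at baseline, after 3 and 6 months and efficacy". The other is the between-group test: "Comparison between both groups for efficacy was done by using Chi square test". The test carries no visit.

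In the results, Table 5 gives the number of patients at each grade, by arm, at baseline, month 3 and month 6. Table 6 ("DISTRIBUTION OF OUTCOME LEVEL n=202") gives one Excellent/Good/Poor split per arm. Table 7 ("COMPARISON OF EFFICACY BETWEEN BOTH GROUPS n=202") tests the corresponding yes/no split, and the stratified Tables 8 to 10 break the same split down. No visit is named in any of these efficacy tables, in STATISTICAL ANALYSIS or in DISCUSSION.

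**The concern.** An outcome defined at two visits should give two responder results, or one result with a stated reason for the choice of visit. Here there is one, undated. The reader cannot tell which time point the conclusion of comparable efficacy refers to, or whether the other time point agrees with it.

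The trial was set up to inform a first-choice treatment, and the timing of improvement bears on that choice. Counts per grade at each visit do not show which patients moved, so Table 5 may not supply the missing responder result.

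**Working it through.** **Inputs.** From Table 5, patients at grades 1/2/3/4:

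| | Baseline | Month 3 | Month 6 |
|---|---|---|---|
| Group A (gel) | 0/0/20/81 | 3/12/26/60 | 3/23/26/49 |
| Group B (microneedling) | 0/0/20/81 | 3/9/22/67 | 3/14/24/60 |

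The narrative in STATISTICAL ANALYSIS prints 50 (59.4%) for group B, grade 4, month 6. Since 60/101 = 59.4%, the 60 in Table 5 is used. From Table 6, Excellent/Good/Poor is 12/25/64 in A and 10/21/70 in B.

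**1. The reported test.** Responders are Excellent plus Good: 12 + 25 = 37 and 10 + 21 = 31. Pearson chi-square without continuity correction on 37/64 v 31/70 gives 0.798, p = 0.372, as printed in Table 7. The difference is 6/101 = +5.9 points. Its standard error is √(0.366×0.634/101 + 0.307×0.693/101) = 0.0664, so the 95% confidence interval is about -7.1 to +18.9 points.

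**2. Grades gained.** The baseline grade sum is 20×3 + 81×4 = 384 in each arm.
- Group A, month 3: 384 - (3 + 24 + 78 + 240) = 39. Month 6: 384 - (3 + 46 + 78 + 196) = 61.
- Group B, month 3: 384 - (3 + 18 + 66 + 268) = 29. Month 6: 384 - (3 + 28 + 72 + 240) = 41.
- Table 6 implies 2×12 + 25 = 49 in A and 2×10 + 21 = 41 in B.

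**3. Which visit is Table 6?**
- *Group B* matches month 6 exactly (41 = 41), and 10/21/70 is among the transition patterns that Table 5 permits at that visit. It fits month 3 only if at least 41 - 29 = 12 of the 20 patients who started at grade 3 worsened.
- *Group A* (49) matches neither 39 nor 61. Month 3 would need at least 49 - 39 = 10 of 20 grade-3 patients to have worsened. Month 6 is impossible. Worsening would only reduce the total, and counting three-grade gains as Excellent adds at most 3, one for each patient at grade 1, giving 52, still below 61.

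**4. Bounds on 3-month responders.** Assume no worsening and gains of at most two grades, as the outcome scale does. Then grades gained = 2E + G, where E and G are the numbers rated Excellent and Good, so responders = E + G = grades gained - E. E is lowest when only the grade-1 patients gained two grades, and highest when every patient now at grade 1 or 2 did.
- A: E from 3 to 3 + 12 = 15, so responders from 39 - 15 = 24 to 39 - 3 = 36.
- B: E from 3 to 3 + 9 = 12, so responders from 29 - 12 = 17 to 29 - 3 = 26.

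The reported 37 and 31 lie above both maxima.

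**5. What the bounds allow at month 3** (uncorrected chi-square, 101 per arm):

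| Responders A v B | Difference (points) | p |
|---|---|---|
| 24 v 17 (both arms at their minimum) | +6.9 | 0.22 |
| 36 v 26 (both arms at their maximum) | +9.9 | 0.13 |
| 24 v 26 | -2.0 | 0.74 |
| 36 v 17 | +18.8 | 0.002 |

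The last two rows need opposite patterns of improvement in the two arms.

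**6. What Table 5 does give at month 3.** Baseline grades are identical in the two arms, so the mean gain is 39/101 = 0.39 grade in A and 29/101 = 0.29 in B. A Mann–Whitney test on the 3-month grades gives p = 0.32.

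**The case against.** The strongest defence is that the analysis text was followed. It promised grade frequencies at each visit, which Table 5 gives by arm, and one efficacy chi-square, which Table 7 gives. Saying that results were noted at both visits is not a promise to test at both. This stands, and it rules out three stronger readings that a reader might infer.

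- *A planned 3-month test was withheld, or reporting was selective.* No passage specifies a between-group test at month 3, and the 3-month grades are published for both arms. What can be said is that the 3-month outcome was recorded but not reported on the responder endpoint.
- *The trial says nothing about early effect.* Table 5 gives 3-month grade distributions and mean gains, and these can be compared. What is missing is the responder form, the only form the trial tests.
- *The gel's advantage at month 3 is larger than the +5.9 points reported.* That sets bounds from Table 5 against a figure from Table 6, and the two tables conflict for group A. On Table 5 alone, the same method at month 6 gives responders of 61 - 26 = 35 to 61 - 9 = 52 in A (at most 17 of the 23 grade-2 patients can have started at grade 3, so E is at least 9) and 41 - 17 = 24 to 41 - 3 = 38 in B. With both arms at their minimum or both at their maximum, the gap is +10.9 to +13.9 points, which exceeds the +6.9 to +9.9 at month 3.

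The lower bounds at month 3 also depend on the two-grade cap. If three patients per arm went from grade 4 to grade 1, a gain for which the scale has no category, they fall to 21 and 14.

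**Conclusion.** The concern holds in limited form. No visit is designated for efficacy, and Tables 6 to 10 carry one unlabelled split. If nobody worsened, that split is not a 3-month result in either arm. Month 6 is supported by group B only; group A's row cannot be a 6-month result if Table 5 is right.

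The 3-month responder difference is known only to lie between -2.0 and +18.8 points, or between +6.9 and +9.9 if both arms sit at the same end of their range. These figures assume that Table 5 is correct as printed, that nobody worsened and that no gain exceeded two grades. Group A's figures are provisional until its two tables agree. The bounds do not show that the 3-month result would change the conclusion. They show that a reader cannot tell whether it supports comparability. The reported result is itself imprecise, with an interval of about -7.1 to +18.9 points.

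This should be corrected, and the data needed are already recorded.

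**What to change.** 1. Reconcile group A's row in Table 6 with Table 5 from the proforma. This comes first, because labelling the present row as month 6 would attach a visit to counts that cannot belong to it.
2. Produce Tables 6 and 7 once for month 3 and once for month 6 with the same Excellent/Good/Poor rule. A baseline-by-visit cross-tabulation of grades for each arm would let readers check both.
3. Label Tables 6 to 10 with their visit.
4. Give the responder difference with a 95% confidence interval at each visit.
5. Present month 6 as the main comparison and month 3 as secondary, and state that this designation was made post hoc, since the documents name no primary visit and results are already known.

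No new visits or measurements are needed. The cost is the record check for group A, the extra tables and one more p-value, which should be marked as secondary.

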**DISTRIBUTION OF SCAR SEVERITY GRADE n=202**

GROUP	GARDE	SCAR SEVERITY GRADE		
		At Baseline	After 3 Months	After 6 Months
GROUP A	1	0 (0%)	3 (3.0%)	03 (3.0%)
	2	0 (0%)	12 (11.9%)	23 (22.8%)
	3	20 (19.8%)	26 (25.7%)	26 (25.7%)
	4	81 (80.2%)	60 (59.4%)	49 (48.5%)
GROUP B	1	0 (0.0%)	3 (3.0%)	03 (3.0%)
	2	0 (0.0%)	9 (8.9%)	14 (13.9%)
	3	20 (19.8%)	22 (21.8%)	24 (23.8%)

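### Efficacy is a change from baseline scar grade but is never shown by baseline grade; the printed counts hint at opposite directions in grades 3 and 4, subject to an unresolved conflict between group A's Tables 5 and 6.

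*Combined protocol and SAP*

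**What the plan says.** Under METHODOLOGY, the outcome is a count of grades gained: "Excellent score was labelled to those patients who uplift by 2 grades, while good for 1 and poor for 0 grade". The methods do not define a responder, but Table 7's efficacy totals equal excellent plus good in Table 6 (12+25=37 in group A, 10+21=31 in group B), so any gain counts.

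The analysis paragraph of the same section names the factors by which efficacy is split: "Modifier like age, gender and time span of disease were organised through stratification". The three stratified tables follow that list. Baseline grade is not among the factors, although it is assessed for every patient and tabulated in Table 5.

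Eligibility covered three grades: "Patients of grade 4 to 2 were estimated by Goodman and Baron scarring scale". Only grades 3 and 4 were enrolled, in identical numbers per arm. STATISTICAL ANALYSIS gives the baseline counts for grades 1 to 4 as "0 (0%), 0 (0%), 20 (19.8%), 81 (80.2%) and 0 (0%),0 (0%), 20 (19.8%), 81 (80.2%) in group A and group B".

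**The concern.** When the endpoint is a change from a starting grade, that grade is an obvious factor to show results by, and here it costs nothing because it is already recorded. The INTRODUCTION says the trial should help identify the better first-choice treatment. If the treatments differed in direction between grade 3 and grade 4 patients, one pooled statement of comparability would be an average of two unlike results, and the reader could not tell. The printed margins allow a partial reconstruction, and it points that way. The same reconstruction shows that group A's outcome tables disagree with each other, which bears on the headline count of 37.

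**Working it through.** **Inputs.** Baseline, both arms: 20 at grade 3, 81 at grade 4 (Table 5). Six-month grades 1/2/3/4 in group A: 3/23/26/49, from Table 5, whose grade 4 row reads "81 (80.2%) 60 (59.4%) 49 (48.5" (baseline, 3 months, 6 months), and from the text, "03 (3%), 23 (22.8%), 26 (25.7%), 49 (48.5". Group B: 3/14/24/60 (Table 5). The text has "14 (13.9%), 24 (23.8%), 50 (59.4" for group B grades 2 to 4, but 60/101=59.4% and the row sums to 101 only with 60, so 60 is used. Responders: 37 and 31 (Table 7).

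**The plan's own figure.** Pearson chi-square on 37/64 against 31/70: 202 × (37×70 - 31×64)² / (101×101×68×134) = 0.798, p=0.372. This matches Table 7.

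**Responders by baseline grade, if nobody worsened.** Everyone at grade 4 at 6 months then started there. Grade 4 responders = 81 minus the 6-month grade 4 count; grade 3 responders = the remainder of the total.

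| Baseline | Group A | Group B | Difference (95% CI) | Chi-square p |
|---|---|---|---|---|
| Grade 4 | 81-49=32/81 (39.5%) | 81-60=21/81 (25.9%) | +13.6 points (-0.7 to 27.9) | 0.065 |
| Grade 3 | 37-32=5/20 (25%) | 31-21=10/20 (50%) | -25 points (-54 to +4) | 0.10 (Fisher 0.19) |

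**Interaction.** Odds ratios: grade 4 (32/49)/(21/60)=1.866; grade 3 (5/15)/(10/10)=0.333. Ratio 5.60, log 1.722. SE = √(1/32+1/49+1/21+1/60+1/5+1/15+1/10+1/10) = 0.763, z=2.26, Wald p=0.024. Breslow-Day gives 0.021. Times four factors: 0.096 and 0.086.

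**Allowing worsening from grade 3 to 4.** Each worsened patient moves one responder from grade 3 to grade 4 in the reconstruction.
- Group B: Table 5's net gain is 384-343=41, and Table 6's is 2×10+21=41. Any worsening must therefore be offset by three-grade gains scored as excellent, of which there can be at most 3 (only three patients reached grade 1). Grade 3 responders are 7 to 10 of 20.
- Group A, from its Table 5 row and 37 responders: 5 minus the number worsened, so 0 to 5 of 20.

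The grade 3 ranges do not overlap, so the direction holds on these inputs. The strength does not: with 1, 2 or 3 worsened in group B only, the ratio is 4.30, 3.29 or 2.51 and the Wald p is 0.056, 0.12 or 0.23.

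**Are the group A inputs consistent?** STATISTICAL ANALYSIS states "Excellent grade was noted in 12 (11.9%) and 10 (9.9%) patients in group A and group B, respectively", and Table 6 adds 25 good in group A.
- Table 5: baseline sum 20×3+81×4=384; 6-month sum 3×1+23×2+26×3+49×4=323; net gain 61.
- Table 6: 2×12+25=49, or at most 49+3=52 if all three grade 1 patients gained three grades. Worsening only lowers this.

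No set of patient transitions fits both. Table 5 with 37 responders and no worsening needs 21 to 24 excellent, not 12.

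**Does the conflict matter?** With 37 responders and no worsening, group A's grade 3 responders = 37-(81-g) = g-44, where g is the true 6-month grade 4 count.
- Row 3/11/38/49 fits Tables 6 and 7 and keeps 5/20: reversal stays.
- Row 3/16/28/54 also fits them: 10/20 against 10/20 in grade 3, 27/81 against 21/81 in grade 4. Ratio of odds ratios 1.43, p=0.62: no reversal.
- If Table 5 and the 12 excellent are right, so that the 37 is wrong, group A has 14 to 17 of 20 in grade 3 and leads in both grades.

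**Is the pooled comparison affected?** Cochran-Mantel-Haenszel: expected group A responders 26.5+7.5=34, observed 37, variance 8.97+2.40=11.37; 3²/11.37=0.791, p=0.374, against the crude 0.372.

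**The case against.** The strongest reply is that the reversal depends on which figures are trusted. It takes Table 7's 37, which is Table 6's 12+25, while setting aside the 12/25 split that contradicts Table 5. Because 37 recurs through the stratified tables, the faulty figure may be group A's Table 5 row, the source of 81-49=32. That stands: the documents cannot settle it. It is also fair that the factor is examined after the results are known, that both within-grade intervals include zero, and that grade 3 rests on 5 against 10 responders.

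A reader might infer that baseline grade limits how far a patient can move on the outcome scale. Among those enrolled it does not: grade 3 to 1 and grade 4 to 2 are both two-grade gains, so all 202 could be rated excellent. The limit would bind only at grade 2, which was eligible but had no patients.

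A reader might also take choosing treatment by severity as the trial's stated purpose. The INTRODUCTION speaks only of a superior first choice; it links treatment choice to scar type, not severity.

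What the objection does not remove is the omission itself, or the value of a transition table. That table would show both the results by baseline grade and which group A figure is wrong.

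**Conclusion.** The point holds as an omission with a provisional signal. Efficacy is never shown by the baseline grade from which it is measured. The printed counts suggest +13.6 points for tazarotene in grade 4 and -25 points in grade 3 (interaction p=0.024), provided that group A's 49 and 37 are both right and nobody worsened. Worsening in group B alone weakens this to p=0.06 to 0.23, and correction for four factors gives about 0.09 to 0.10.

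The tempting stronger reading is that the trial's tables establish a reversal hidden by the pooled conclusion. They do not, because group A's Tables 5 and 6 cannot both be right (61 grades gained against at most 52) and some reconciliations give no reversal. Nor is the pooled test confounded by baseline grade, which is 20 and 81 in each arm; the question is effect modification only. Separately, if the reconciliation changes the 37, the headline result changes with it.

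**What to change.** 1. From the proforma, reconcile group A's Tables 5 and 6. If the counts change, correct Tables 6 and 7, the p-value of 0.372, the stratified tables and every place that repeats them.
2. Report, for each arm, a table of baseline grade by 6-month grade, including any worsening.
3. Add baseline grade (3 against 4) as a factor labelled post hoc and exploratory, with the efficacy difference and 95% CI in each grade and one arm-by-grade interaction test.
4. Keep the overall comparison as the main result. Mention any difference by grade only as hypothesis-generating, given 20 grade 3 patients per arm; do not reword the conclusions by grade.

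The cost is a check of existing records, one table per arm and one further exploratory comparison. No new data are needed.
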